8.2 Determination of Sample Size and Accrual Rate

8.2.1 Sample Size and Power Estimate

The primary endpoint is to evaluate the positive predictive value (PPV) on a (1) per-patient and (2) per-region-basis (prostate bed, pelvis, extrapelvic soft tissue, and bone metastases) of ⁶⁸Ga-PSMA-11 PET for detection of tumor location confirmed by histopathology/biopsy. Based on the results of previous studies, the following distribution of disease across the four regions are anticipated (19-21):

- a) Prostate bed: 30%
- b) Pelvis: 15%
- c) Extrapelvic soft tissue: 20%
- d) Bone metastases: 35%

It is anticipated that the PPV for the four regions and for all regions combined using conventional imaging ranges from 30-60%. An overall PPV for ⁶⁸Ga-PSMA-11 PET of at most 50% will be considered as unacceptably low. Hence, the null hypothesis that the PPV is at most 50% will be tested against the alternative hypothesis that the PPV is greater than 50%. It is hypothesized that ⁶⁸Ga-PSMA-11 PET imaging on the per-region and per-patient basis will substantially increase the PPV for the four regions to at least 70%. A sample size of 75 true positives is required for rejecting the null hypothesis that the PPV is at most 50% with 90% power at the one-sided 0.01 (=0.05/5 – a Bonferroni adjustment for evaluating the PPV for the four regions and for all regions combined) significance level, assuming an average regions specific prevalence of 20%. It is expected that approximately 25% of the accrued patients will undergo a biopsy. Hence, the proposed total number of patients requiring a biopsy is 375 in

order to power the analysis at a per region level. Assuming a prevalence rate of 20% for disease in each individual region, a total sample size of 1,500 patients is required. The following table shows the attainable power levels for detecting an increase in the PPV from 50% to 70% at the one-sided 0.01 significance level for the four disease regions and for all regions combined with the proposed sample size of 1500 patients:

Table: *Attainable power levels for detecting an increase in PPV from 50% to 70% with sample size of 1,500 patients (375 biopsies)*

	Prevalence	Number of Biopsies with True Positives	Power
Prostate bed	30%	113	98%
Pelvis	15%	56	78%
Extrapelvic soft tissue	20%	75	90%
Bone metastases	35%	131	>99%
All regions combined	100%	375	>99%

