8.3.2 Analysis of Primary Endpoints

PPVs on a per-patient and per-region-basis of ⁶⁸Ga-PSMA-11 PET for detection of tumor location confirmed by histopathology/biopsy will be calculated and reported along with the corresponding two-sided 95% confidence intervals. The confidence intervals will be constructed using the Wilson score method.

a) Imaging interpretation ⁶⁸Ga-PSMA-11 PET:

PET images will initially be interpreted by a board certified nuclear medicine physician or a board certified radiologist experienced in reading PET at the time of the imaging study at the institution that the study is being performed. These interpretations will not be used for final evaluation. For the data sets included in the analysis for the Primary Endpoint, imaging data will be anonymized and collected at a central site. PET data will be interpreted by three different readers in a random order at separate reading sessions. ⁶⁸Ga-PSMA PET/CT reading training set and guides will be provided and completion of this training will be required for all central review readers.

Visual interpretation:

Regions of suspected disease will be graded on a two-point scale by each reader (0=Negative or 1= Positive). A region will be judged as positive if at least one lesion in this region is visually positive.

- i) Lymph nodes will be considered positive if the ^{68}Ga -PSMA-11 uptake is focal and greater than blood pool (adjacent or mediastinal blood pool). Pelvic lymph nodes will be subclassified according to their localization as follows: R/L obturator, R/L external iliac, R/L internal iliac and other (total of 7 subgroups).
 - ii) Visceral lesions will be considered positive if the ^{68}Ga -PSMA-11 uptake is focal and greater than physiologic background activity of the involvement organ or anatomic site.
 - iii) Bone lesions will be considered positive if the ^{68}Ga -PSMA-11 uptake is focal and greater than physiologic bone marrow.
 - iv) Prostate bed and prostate lesions will be considered positive if the ^{68}Ga -PSMA-11 uptake is focal and greater than physiologic background activity of the involvement organ or anatomic site.
- b) Follow-up Imaging:

All patients will be followed up 3-12 months with conventional imaging (dedicated CT, MRI and/or bone scan). Interpretation of follow-up imaging will be performed by local read. The follow-up conventional imaging should be the same modality/modalities as the initial staging work-up to allow for reproducible and accurate comparisons.

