- iii) ⁶⁸Ga-PSMA-11 positive bone lesions will be considered:
- (1) True positive:
- If there was a corresponding positive sclerotic lesion on the CT portion of the ⁶⁸Ga-PSMA-11 PET.
 - If there is focal uptake seen on the baseline bone scan performed within one month of ⁶⁸Ga-PSMA-11 PET.
 - If there is a lesion noted on the initial MRI performed within one month of ⁶⁸Ga-PSMA-11 PET.
 - If within 12 months follow-up CT demonstrates development of sclerosis.
 - If within 12 months follow-up MRI demonstrates a new bone lesion.
 - If within 12 months follow-up bone scan demonstrates new focal uptake.
- (2) False positive:
- If ⁶⁸Ga-PSMA-11 positive bone lesions do not meet the criteria for true positive findings.
- iv) ⁶⁸Ga-PSMA-11 positive prostate bed and prostate lesions will be considered:

(1) True positive:

- If on follow-up imaging within 12 months, lesions seen on CT or MRI decrease by 30% (for patients undergoing systemic treatment of focal therapy at this site) or increase by 20% in largest diameter..
- If patients with prostate bed lesions show a decrease of PSA by greater than 50% after targeted treatment (i.e. external beam radiation) and lesions do not change in size (less than 30% decrease or 20% increase in largest diameter).

(2) False positive:

- If on follow-up imaging within 3-12 months, sites of initial⁶⁸Ga-PSMA-11 positive lymph node lesions seen on CT or MRI decrease by more than 30% *without* systemic therapy or focal therapy at this site.
- If ⁶⁸Ga-PSMA-11 positive lymph node lesions do not meet the criteria for above false positive or true positive findings.

c) Histopathology/Biopsy:

- i) Localization of lesions for histopathology/biopsy will be classified according to the regions in table 1.
- ii) ⁶⁸Ga-PSMA-11 positive findings are aimed to be confirmed by histopathology/biopsy if clinically feasible.
- iii) Histopathological procedures and biopsies will be performed as clinically indicated and as per institutional protocol.

(1) Positive HP/Biopsy: Confirmed sites of metastatic or tumor involvement by histopathology/biopsy will be discussed with the responsible physician/surgeon.

(2) Negative Biopsy: Patients with suspected tumor recurrence on ⁶⁸Ga-PSMA-11 PET with negative histopathology/biopsy will be handled as outlined below:

(a) Lymph nodes:

- For patients undergoing nodal dissection: Patients will be rescanned with dedicated CT or MRI to determine if the suspicious ⁶⁸Ga-PSMA-11 positive node was removed.

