 1. If ⁶⁸Ga-PSMA-11 positive lymph node is still present, a repeat biopsy can be pursued if clinically feasible and applicable, or follow-up using imaging as described above will be performed.
 2. If the corresponding node was removed, then this will be considered a False Positive.
- For patients undergoing needle biopsy: Images of the procedure will be reviewed to determine if the correct node was biopsied.
 1. If the correct node was biopsied, then a negative biopsy will be considered a False Positive.

2. If the incorrect node was biopsied, then follow-up imaging as described above will be performed.
 - (b) Bone lesions: Given the high rate of false negative biopsies for osseous metastases in patients with prostate cancer, patients with negative bone biopsies of PSMA PET positive lesions will be further evaluated:
 - If pathology demonstrates an alternative diagnoses that is known to be PSMA positive (eg Renal Cell Carcinoma metastases, Paget's disease), then this will be considered a False Positive.
 - If pathology is indeterminate, then follow-up imaging as described above will be performed to determine if the lesion is a True Positive or False Positive.
 - (c) Additionally a repeat ^{68}Ga -PSMA-11 can also be obtained, as allowable, in addition to repeat conventional imaging (CT and/or MRI) in cases of negative biopsy to determine if the biopsy was true negative or false negative.
 - (d) Although not routinely performed during standard practice, immunohistochemical staining for PSMA of tumor specimens (primary and lymph node metastases) may be performed, although not required.

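### Lymph-node specimens are checked for whether the PET-positive node was sampled only when histology is negative, which can inflate the biopsy-only PPV in the node regions

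*Combined protocol and SAP*

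**What the plan says.** Sections 2.1, 8.2.1 and 8.3.2 define the primary PPV, per patient and per region, against histopathology or biopsy. Section 8.3.1 restricts the primary analysis to patients with a histopathology correlate. Adding conventional imaging follow-up to the reference standard is a secondary objective (sections 2.2 and 8.3.3).

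The rules in section 8.3.2 c) differ by result:

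- **All specimens, location:** "Localization of lesions for histopathology/biopsy will be classified according to the regions in table 1". Under 8.3.2 a), a region is PET-positive if any single lesion in it is.
- **Positive specimen:** "Confirmed sites of metastatic or tumor involvement by histopathology/biopsy will be discussed with the responsible physician/surgeon". No step asks whether the tissue came from the PET-positive lesion.
- **Negative node, dissection:** the patient is rescanned to see whether the PET-positive node was removed. If it was, the result is a false positive. If it is still there, the case goes to optional repeat biopsy or imaging follow-up.
- **Negative node, needle biopsy:** procedure images are reviewed. If the right node was sampled, the result is a false positive. Otherwise: "If the incorrect node was biopsied, then follow-up imaging as described above will be performed".

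Readers also assign PET-positive pelvic nodes to subgroups ("R/L obturator, R/L external iliac, R/L internal iliac and other (total of 7 subgroups"), but nothing links the histology to them.

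**The concern.** Whether a specimen's location is questioned depends on its result. A node specimen that missed its target is set aside if benign but stays in the analysis as a success if it contains tumour. That is selection on outcome within the primary endpoint.

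The PPV is formally tested: "the null hypothesis that the PPV is at most 50% will be tested against the alternative hypothesis". Selection that works only in favour of the product would raise both the estimate and the chance of wrongly rejecting that null. The exposure lies in region 2 (pelvis) and the nodal part of region 3, and in diluted form in the combined and per-patient PPV. Section 1.1 says that the data are to be pooled for a marketing application, so the counting rule should be settled before the data are read.

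**Working it through.** **The plan's own figure.** Section 8.2.1 gives a null PPV of 50%, an alternative ("will substantially increase the PPV for the four regions to at least 70" per cent), and a test "with 90% power at the one-sided 0.01 (=0.05/5" for five tests). The one-sample normal approximation is

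n = [(z₀.₉₉·√(0.5·0.5) + z₀.₉₀·√(0.7·0.3))/0.2]² = [(2.326·0.5 + 1.282·0.458)/0.2]² = 76.6.

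The plan states 75 ("A sample size of 75 true positives is required for rejecting the null hypothesis"). The same formula gives power of 98.2%, 76.7%, 89.3%, 99.3% and over 99.9% at n = 113, 56, 75, 131 and 375. The plan's table has 98%, 78%, 90%, >99% and >99%. The sample size reproduces and is not in dispute.

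**Bias model.** Let p be the true PPV among on-target specimens, w the share of node specimens that are off-target, and q the chance that an off-target specimen holds tumour. The documents give neither w nor q, so the values below are assumptions. If off-target negatives leave the primary analysis and off-target positives stay:

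apparent PPV = [(1−w)p + wq] / [(1−w) + wq], and bias = wq(1−p) / [(1−w) + wq].

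The bias is above zero whenever w > 0, q > 0 and p < 1. At p = 50%:

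- (10%, 30%): 0.48/0.93 = 51.6%
- (20%, 50%): 0.50/0.90 = 55.6%
- (30%, 50%): 0.50/0.85 = 58.8%

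Keeping every specimen as a region-level result gives (1−w)p + wq = 48.0%, 50.0% and 50.0%. The selected figure is therefore too high for a purely regional estimand as well.

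**False rejection, pelvis.** The planned n is 56. The exact one-sided 0.01 test rejects at 38 or more (size 0.5%). With n held fixed, the rejection probabilities are in the table. The plan does not name its test. Under a normal approximation (size 1%), the first two pairs give 1.8% and 6.6%.

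**False rejection, all regions combined.** The location check covers nodes only. The plan expects 15% pelvis and 20% extrapelvic soft tissue, so nodes are at most 15% + 20% = 35% of specimens, and fewer if region 3 includes organ lesions. With the other 65% unaffected:

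apparent PPV = {0.65p + 0.35[(1−w)p + wq]} / {0.65 + 0.35[(1−w) + wq]}.

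This gives 0.493/0.9755 = 50.5%, 0.500/0.965 = 51.8% and 0.500/0.9475 = 52.8%. At n = 375 the exact test rejects at 211 or more (size 0.9%).

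| w, q (assumed) | Apparent node PPV | False rejection, n = 56 | Apparent PPV, all regions | False rejection, n = 375 |
|---|---|---|---|---|
| no bias | 50% | 0.5% | 50% | 0.9% |
| 10%, 30% | 51.6% | 1.0% | 50.5% | 1.5% |
| 20%, 50% | 55.6% | 4.2% | 51.8% | 4.7% |
| 30%, 50% | 58.8% | 10.7% | 52.8% | 9.6% |

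**Alternative reading.** Suppose instead that off-target negatives are classified by imaging and counted in the primary analysis, with chance s of being called true positive. Then PPV = (1−w)p + w[q + (1−q)s]. At p = 50%, w = 10%, q = 30%, this is 48.0% at s = 0, 49.4% at s = 20% and 51.5% at s = 50%. The break-even is s = (p−q)/(1−q) = 0.2/0.7 = 0.29.

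**The case against.** The strongest reply is that the plan nowhere says off-target negatives are dropped. It sends them to imaging or optional repeat biopsy. The imaging rules sit inside 8.3.2, the primary-endpoint section, and a node that meets neither imaging definition defaults to false positive. A repeat biopsy can also return a false positive. All of this stands. That these cases leave the primary analysis is an inference from the histopathology-only reference standard and population; on the other reading the bias can be small or negative.

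A second reply is that the estimand is regional, so tumour in a different node of a PET-positive region is a legitimate true positive. That is also right. A reader might infer that such results are misclassified and that positives must match by side and subgroup; the documents do not support this. Nor would such a match equal the node-level check applied to negatives. The regional argument does not rescue the asymmetry, however: if an off-target positive informs about the region, so does an off-target negative.

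Two wider readings also fail:

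- **Bone and prostate bed.** The bone rule turns on what the pathology shows (an alternative diagnosis or an indeterminate result), not on whether the right lesion was sampled. There is no location-based exclusion for the prostate bed. The asymmetry does not arise in either.
- **The whole biopsy set.** Applying the same w to all 375 specimens would suggest false rejection of 4%, 41% and 86%. That treats every specimen as a node; at the 35% ceiling the figures are those in the table.

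Finally, section 8.3.2 c) ii) makes PET-positive findings the intended biopsy target, which argues for a modest w.

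**Conclusion.** The concern holds for lymph nodes: region 2 and the nodal part of region 3. The one-sided check is in the text, and if off-target negatives leave the histopathology-only primary analysis, PPV is biased upward. The size depends on w and q, which the documents do not give. It is negligible when off-target sampling is rare, and takes the pelvic false-rejection rate to about 4% to 11% under the two heavier assumptions, against a nominal 1%. For all regions combined those two give at most about 5% to 10%.

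A reader might conclude that the plan certainly inflates its PPV. The documents do not establish that, because they never say how off-target negatives are counted. What they establish is a result-dependent check on a tested endpoint and a missing counting rule, on which the direction of the bias depends. This should be fixed; it does not invalidate the design.

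**What to change.** In 8.3.2 c) iii), use one rule for node specimens whatever the histology:

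1. Judge on-target status for every node specimen from existing pathology reports and procedure images, or post-procedure images where available. The assessor should be blinded to histology, for example by working from specimen-site labels with the result masked. The pelvic subgroups already recorded can help but do not identify a node on their own.
2. Treat off-target positives and off-target negatives alike in the histopathology-only primary analysis: either exclude both, or keep both as region-level results. State which is primary and report the other as a sensitivity analysis.
3. Say how specimens of undeterminable location are handled, identically for both results. This matters because the plan calls for a rescan only after a negative dissection, so on-target status will be easier to settle for negatives.

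The cost is wording and a review of material that largely exists; pathology reports may not always label sites finely enough. If both kinds are excluded, the denominator shrinks and the interval widens: 10% off-target takes the pelvis from n = 56 to about 50, and power by the normal approximation from about 77% to 71%. Keeping both costs no sample size, but then the PPV refers to the region and not to the node seen on PET.

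### The bone biopsy rule gives no outcome to some definite benign diagnoses and sends indeterminate samples to imaging criteria that baseline findings can satisfy, so the histology-based bone PPV can be biased by an unknown amount

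*Combined protocol and SAP*

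**What the plan says.** The primary PPV is defined against histopathology or biopsy (sections 2.1, 8.2.1 and 8.3.2). Histopathology together with conventional imaging follow-up is a separate, secondary standard (sections 2.2 and 8.3.3).

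Section 8.3.2 c) (2) sets out what happens when a PET-positive lesion has a negative biopsy.

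- Nodes, needle biopsy: "If the correct node was biopsied, then a negative biopsy will be considered a False Positive". A wrongly targeted node goes to imaging follow-up.
- Bone, first route: "If pathology demonstrates an alternative diagnoses that is known to be PSMA positive", the lesion is a false positive. Renal cell carcinoma metastasis and Paget's disease are the examples.
- Bone, second route: "If pathology is indeterminate, then follow-up imaging as described above will be performed to determine if the lesion is a True Positive or False Positive".

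The reason given for treating bone separately is that biopsies of osseous metastases are often falsely negative. No rate is stated.

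The imaging rule for bone, earlier in 8.3.2, lists six true-positive criteria. Three are baseline findings. One begins "If there was a corresponding positive sclerotic lesion on the CT portion of the" PSMA PET, another begins "If there is focal uptake seen on the baseline bone scan performed within one month of" the PET, and the third is a lesion on an MRI done within a month of the PET. Otherwise the lesion is a false positive, because the default applies when "positive bone lesions do not meet the criteria for true positive findings".

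Section 8.2.1 plans for "Bone metastases: 35"% of disease, which is 131 of 375 biopsies. Bone is one of five hypotheses, each tested at one-sided 0.01 against a PPV of 50%.

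**The concern.** The two bone routes do not cover every negative result. An on-target biopsy that shows a definite benign process is neither indeterminate nor, unless the process is a known PSMA-positive entity, a false positive under the first route. The same kind of result in a node is scored against the scan. If such bone results go unscored, false positives leave the denominator while every positive biopsy stays in.

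The second route raises a different problem. Imaging follow-up is meant to settle a sample that histology could not settle. Yet sclerosis on the CT of the same PET study, uptake on a baseline bone scan or a lesion on a baseline MRI is enough for a true positive, with no change over time. Whether that verdict counts in the primary PPV or only in the secondary one is not said.

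At stake is the type I error of the test in the largest region and, through it, of the all-regions test. Section 1.1 says the pooled data are meant to support an NDA.

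**Working it through.** **Plan's own figure.** Inputs from 8.2.1: null 50%, alternative 70%, one-sided 0.01, n = 35% × 375 = 131. By the normal approximation, power = Φ{[(0.70 − 0.50) − 2.326 × √(0.25/131)] / √(0.21/131)} = Φ(0.0984/0.0400) = 99.3%. The plan states above 99%, so it reproduces. The exact binomial test rejects at 80 or more of 131 (61.1%), with type I error 0.7% and power 98.9%. These figures assume that every biopsied bone lesion is scored correctly.

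**Model when unscored biopsies are dropped.** The plan gives no rates, so both parameters are assumptions:

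- P = true PPV, set to the null value of 50%
- g = share of truly malignant lesions with a falsely negative biopsy, which are dropped
- f = share of truly negative biopsies scored false positive; the rest are dropped

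Scored share D = P(1 − g) + (1 − P)f. Number scored = 131 × D. Observed PPV = P(1 − g)/D. Rejection is the exact binomial tail at nominal one-sided 0.01 for that n.

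| g | f | D | n | Observed PPV | Reject if at least | P(reject) |
|---|---|---|---|---|---|---|
| 0 | 100% | 1.000 | 131 | 50.0% | 80 | 0.7% |
| 0 | 90% | 0.950 | 124 | 52.6% | 76 | 3.2% |
| 0 | 75% | 0.875 | 115 | 57.1% | 71 | 18% |
| 0 | 50% | 0.750 | 98 | 66.7% | 61 | 85% |
| 20% | 80% | 0.800 | 105 | 50.0% | 65 | 0.9% |
| 20% | 50% | 0.650 | 85 | 61.5% | 54 | 40% |
| 30% | 75% | 0.725 | 95 | 48.3% | 60 | 0.3% |

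The observed PPV equals the true PPV when f = 1 − g. It is too high when f > 0 is smaller than 1 − g, and too low when f is larger.

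**If imaging-resolved lesions do enter the primary PPV.** Suppose a share c of truly negative lesions becomes true positive through a baseline finding, the rest are scored false positive, and g = 0. Observed PPV = 0.5 + 0.5c. For c = 10%, 20% and 30% this gives 55%, 60% and 65%, with rejection 9.5%, 44% and 85% at n = 131.

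**All regions combined.** Take the other 65% of biopsies as correctly scored, with g = 0 and the drop model for bone. D = 0.65 + 0.35 × (0.5 + 0.5f). For f = 75% and 50%, D is 0.956 and 0.9125, n is 359 and 342, observed PPV is 52% and 55%, and rejection is 6% and 29%.

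**The case against.** The strongest defence is the protocol's own reason. If bone biopsies often miss tumour, counting every negative one as a false positive biases the PPV downward. At a true PPV of 70% and g = 20%, the strict rule gives an observed PPV of 0.70 × 0.80 = 56%, and the power at n = 131 falls to 14%. This stands. It is why bone may be handled differently from nodes, and why the rows with g = 0 cannot be read as the effect size.

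Two stronger readings are tempting. A reader might infer that a known PSMA-positive diagnosis is the only way for a negative bone biopsy to become a false positive. The documents do not say this: indeterminate samples go to imaging, where false positive is the default. A reader might also infer that bone PPV is driven towards 100% by design. That would need no negative lesion at all to be scored false positive, and the documents give no breakdown of negative bone pathology that would support it.

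It can also be said that 8.3.2 c) (2) (c) allows repeat PSMA PET and conventional imaging after any negative biopsy. That provision is optional and assigns no outcome. It also lets the test under study help to judge its own reference standard.

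What the defence does not reach is the definite alternative diagnosis. A high miss rate is a reason to treat non-diagnostic tissue as unresolved. It is not a reason to leave a benign diagnosis that explains the uptake unscored because the entity is not already known to be PSMA positive.

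**Conclusion.** The concern holds in this form: the rule for negative bone biopsies is incomplete, differs from the node rule beyond what its stated reason supports, and does not say which PPV takes lesions settled by imaging. Leaving definite benign diagnoses unscored, or letting baseline imaging overturn a biopsy, moves bone PPV up. Dropping falsely negative biopsies moves it down. In the dropped-sample scenarios worked here, the true error rate of a nominal 1% test ranges from 0.3% to 85%. The range reflects the assumed f and g, not an estimate, and the documents do not allow even the net direction to be fixed. The stated power for bone is reproduced and is not in dispute. What is at risk is the estimate and the error rate of a primary test, so the rule should be settled before the data are scored.

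**What to change.** In 8.3.2 c) (2) (b), give every negative bone result an outcome:

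1. An on-target bone biopsy with any definite alternative (non-prostate-cancer) diagnosis is a false positive, whether or not that diagnosis is known to be PSMA positive.
2. A non-diagnostic sample, including normal bone or marrow that does not explain the uptake, is unresolved by histology.
3. A lesion resolved by imaging counts only in the secondary composite PPV.
4. The bone and combined histology PPV are each reported twice: with unresolved biopsies excluded, and with them counted as false positive.

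The second version in item 4 is a conservative lower bound, because it counts falsely negative biopsies as false positives. The first is not a strict upper limit, since excluding falsely negative samples can itself lower the PPV. The pair should be read as showing how far the result depends on unresolved samples.

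The cost is a reworded rule and an extra row in the PPV table, with no added procedures. Bone PPV may come out somewhat less favourable.

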8.3 Analyses Plans

8.3.1 Analysis Population

Patients with histopathology correlates will be analyzed for the Primary Aim. All remaining patients will be analyzed for the secondary endpoints.

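### Section 8.3.2 does not say which PPV takes imaging verdicts on biopsied lesions, lets a repeat PSMA PET inform its own reference standard, and names the wrong lesion type in two false-positive rules

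*Combined protocol and SAP*

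**What the plan says.** **Reference standards.** Sections 2.1, 8.2.1 and 8.3.2 define the primary PPV against histopathology/biopsy. Sections 2.2 and 8.3.3 define a secondary PPV against biopsy and conventional imaging follow-up. Section 8.3.2 b) lists that imaging as CT, MRI and/or bone scan; PSMA PET is not included.

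**Population.** Section 8.3.1: "Patients with histopathology correlates will be analyzed for the Primary Aim". The remaining patients go to the secondary endpoints.

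**Negative biopsies.** Section 8.3.2 c) (2) says that patients with suspected recurrence on "PET with negative histopathology/biopsy will be handled as outlined below". The branches are:
- Dissection, PET-positive node still present: repeat biopsy, "or follow-up using imaging as described above will be performed".
- Dissection, node removed: False Positive.
- Needle biopsy on target: "If the correct node was biopsied, then a negative biopsy will be considered a False Positive".
- Needle biopsy off target: "If the incorrect node was biopsied, then follow-up imaging as described above will be performed".
- Bone, alternative PSMA-positive diagnosis: False Positive.
- Bone, other: "If pathology is indeterminate, then follow-up imaging as described above will be performed", and the result decides true or false positive. The reason given for further evaluation of negative bone biopsies is "Given the high rate of false negative biopsies for osseous metastases in patients with prostate cancer".
- Item (c), any negative biopsy: a repeat 68Ga-PSMA-11 scan may be obtained together with repeat conventional imaging ("CT and/or MRI) in cases of negative biopsy to determine if the biopsy was true negative or false negative").

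**Imaging false-positive rules.** In 8.3.2 b), the rules for visceral lesions (ii) and for prostate-bed and prostate lesions (iv) repeat the lymph-node text and name only lymph node lesions.

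**The concern.** Three matters need separating.

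1. *Allocation.* The imaging branches sit under the heading for the primary endpoints, while the primary reference is biopsy alone. Section 8.3.1 allocates patients, not lesion verdicts. A biopsied patient whose lesion was finally judged by imaging falls, read literally, in the primary set. Whether that verdict replaces the biopsy result, removes the lesion from the primary PPV, or counts only in the secondary PPV is not stated.

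2. *Circularity.* Where item (c) is used, the test under evaluation helps to decide whether its own reference was wrong. Neither stated reference includes PSMA PET. Item (c) gives no decision criterion, and it covers all negative biopsies, so it could reopen an on-target nodal negative that item (a) has already called a False Positive.

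3. *A wrong rule.* Read literally, a visceral or prostate-bed lesion can never be false positive on imaging, because the false-positive rules under those stems apply only to lymph nodes. This chiefly affects the secondary PPV.

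At stake is the numerator and denominator of a PPV that section 8.2.1 tests against 50%, region by region, at one-sided 0.01. Section 1.1 intends the data to be pooled across institutions, so sites need one rule.

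**Working it through.** **Step 1: the plan's own figures.** Section 8.2.1 gives a null of 50%, an alternative of 70%, one-sided alpha 0.01, 90% power and n = 75. With the normal approximation:

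n = [(z(0.99)·√(0.5×0.5) + z(0.90)·√(0.7×0.3)) / 0.2]² = [(2.326×0.5 + 1.282×0.458) / 0.2]² = 76.6, so 77 against 75 stated.

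The same formula gives power of 98.2%, 76.7%, 89.3%, 99.3% and >99.9% at n = 113, 56, 75, 131 and 375. The plan states 98%, 78%, 90%, >99% and >99%. The figures reproduce to within two patients and two percentage points, so this point rests on no arithmetic error.

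**Step 2: the branches against the two definitions.**

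| Negative-biopsy outcome | What the plan does | Which PPV takes the verdict |
|---|---|---|
| Node removed; correct node sampled; alternative PSMA-positive bone diagnosis | False Positive | Follows from histopathology |
| Node still present; wrong node; indeterminate bone pathology | Imaging (or repeat biopsy for a retained node) | Not stated |
| Plainly benign bone biopsy; negative visceral or prostate-bed biopsy | No rule except optional (c) | Not stated |
| Any negative biopsy, item (c) | Repeat PSMA PET plus CT and/or MRI, optional | Not stated; the PSMA PET part fits neither definition |

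**Step 3: how much the allocation could matter (illustration).** Inputs:
- n = 131 for bone, from the power table in 8.2.1, taken here as biopsied PET-positive regions (assumption).
- p = PPV among the other biopsies, set at the planned 70%.
- u = share of bone samples that are indeterminate; t = share of those that imaging calls true positive. The documents give neither, so u = 10% or 20% and t = 30%, 60% or 90% are assumed.
- Exact binomial test (the plan names no test). The critical value at one-sided 0.01 is 80 of 131, with exact size 0.0071.

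Formulas: PPV if excluded = p. PPV if imaging-resolved = p(1−u) + u·t. The difference, imaging-resolved minus excluded, is u(t−p), which can have either sign. For u = 20% and t = 30%: 0.7×0.8 + 0.2×0.3 = 0.62.

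| u | Excluded: PPV, power | t = 30% | t = 60% | t = 90% |
|---|---|---|---|---|
| 10% | 70%, 98.1% | 66%, 89.9% | 69%, 97.9% | 72%, 99.7% |
| 20% | 70%, 96.4% | 62%, 62.4% | 68%, 96.2% | 74%, >99.9% |

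The excluded column averages the exact test over the binomial number of samples kept.

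**Step 4: the same with p = 50%.** Rejection is 0.8% if excluded. It is 0.2%, 1.3% or 6.2% if imaging-resolved at u = 10%, and 0.04%, 2.3% or 26.8% at u = 20% (t = 30%, 60%, 90%).

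**The case against.** **The definitions may already settle allocation.** An imaging verdict fits only the secondary definition. A wrong-node or retained-node sample yields no histology of the PET lesion, so it is arguably no histopathology correlate under 8.3.1. Placement in 8.3.2 proves little, because that section also holds the imaging criteria that the secondary PPV needs. Much of this stands, and the secondary PPV is the better-supported reading. But it has to be inferred. Even on that reading, the plan does not say whether off-target and indeterminate samples leave the primary PPV or count against it.

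**Item (c) is weak.** It is optional, is paired with conventional imaging, and asks about the biopsy rather than expressly setting lesion status. This also stands. A reader might infer that it converts negatives to true positives. If 5%, 10% or 20% of all bone negatives were overturned at a 50% biopsy PPV, rejection would be 3.0%, 9.5% or 43.9%. The text does not say that it does this, so those figures are not the size of this point. What remains is that nothing rules such use out.

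**A stronger reading of the numbers is tempting.** Counting all indeterminate bone samples as False Positive at u = 20% gives a PPV of 0.7×0.8 = 56% and power of 14.0%. No passage proposes that for the primary analysis; it belongs in a sensitivity row only. Likewise, the 26.8% in step 4 might be read as type I error inflation. It is not: the imaging-resolved PPV there is 58%, and if imaging is right about those lesions the null is false. The plan itself warns that bone biopsies miss tumour.

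**The lymph-node wording is an evident copying slip.** It is, and the intention can be guessed from the stems. It is still the operative rule as written.

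**Conclusion.** The point holds in a limited form. The text leaves open which PPV receives imaging verdicts on biopsied lesions, with the definitions favouring the secondary. It permits the index test to inform its own reference standard, outside both definitions and in tension with the on-target nodal rule. It also contains two imaging false-positive rules that name the wrong lesion type.

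The numerical effect is conditional on assumed shares. Between the two better-supported readings, excluded and imaging-resolved, bone power is almost the same when imaging calls 60% of indeterminate samples true positive (96.4% versus 96.2% at 20% indeterminate). It separates clearly only when that share is far from the PPV of the other samples: 62.4% at t = 30% with 20% indeterminate, 89.9% with 10%. The direction can go either way.

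The documents do not show an inflated type I error, nor that imaging re-judgement moves the PPV away from true disease status. What they show is that a tested result depends on a rule that is not written down.

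**What to change.** 1. State that a repeat 68Ga-PSMA-11 scan does not set true or false positive status in either PPV, and reconcile item (c) with item (a) of the negative-biopsy rules. This concerns classification only, not whether a scan is done.
2. State that imaging verdicts on biopsied lesions count only in the composite secondary PPV. In the primary PPV, count a diagnostic negative biopsy as False Positive; for nodes, do so when the targeting check already in 8.3.2 c) confirms that the PET-positive node was sampled. Report off-target nodal and indeterminate bone samples as excluded, with one sensitivity row counting them as False Positive and one using the imaging-resolved status.
3. In the visceral and prostate-bed imaging false-positive rules, replace the lymph-node wording with the lesion type in question.

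No targeting requirement is asked for outside lymph nodes, because the plan provides no image review there. The bone true-positive criteria in 8.3.2 b) iii) are left as listed.

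The cost is SAP wording and extra rows in the PPV table, using data that the plan already collects. The downside is that the bone PPV may look less favourable where biopsies miss tumour; the side-by-side rows show by how much.
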